5.2 Criteria for Starting Subsequent Cycles

A cycle may be repeated every 21 days if the patient has again met laboratory parameters as defined in the eligibility section, [Section 4.0](#), or is eligible to continue agent administration per the requirements in [Section 6.0](#). For cycles 3 and later, patients must also have at least stable disease while meeting the criteria established in [Section 4.0](#) and meets the requirements presented in [Section 6.0](#).

5.3 Dose Escalation Schema

5.3.1 Inter-Patient Escalation

The starting dose of ABI-009 will be 35 mg/m² (dose level 1) with dose levels for subsequent groups of patients as follows.

Dose Level	Cycle 1	Cycle 2+		
	ABI-009 (mg/m ²)	ABI-009 (mg/m ²)	Irinotecan (mg/m ²)	Temozolomide ** (mg/m ²)
-2 [^]	15	15	90	125
-1	20	20	90	125
1*	35	35	90	125
2	45	45	90	125
3	55	55	90	125

* Pre-Amendment #4: Starting dose level is the RP2D from COG study ADVL0918.

** Maximum temozolomide dose = 250 mg/dose

[^] Amendment #4: Starting dose level

There will be no planned escalations beyond dose level 3 (55 mg/m²), as previous pediatric Phase 1 studies have rarely defined an MTD greater than 160% of the adult MTD. However, if evaluation of PK and toxicity data as well as additional data from adult studies suggest higher doses are required to achieve maximal potential benefit, an amendment to the trial will be considered to add additional dose levels.

Amendment #4:

DL- 2 will be evaluated with modified definitions of hematological DLT, and there will be no planned escalations beyond dose level -2. If DL -2 is not well tolerated further de-escalation will not occur. The study will be closed to accrual.

5.3.2 Intra-Patient Escalation

Intra-patient dose escalation is not allowed.

5.4 Grading of Adverse Events

Adverse events (toxicities) will be graded according to the NCI Common Terminology Criteria for Adverse Events (CTCAE) version 5.0. All appropriate treatment areas should have access to a copy of the CTCAE version 5.0. A copy of the CTCAE version 5.0 can be downloaded from the CTEP website (<http://ctep.cancer.gov>). Any suspected or confirmed dose-limiting toxicity should be reported immediately (within 24 hours) to the Study Chair.

5.5 Definition of Dose-Limiting Toxicity (DLT)

DLT will be defined as any of the following events that are possibly, probably or definitely attributable to protocol therapy. The DLT observation period for the purposes of dose-escalation will be Cycles 1 and 2 of therapy.

Dose limiting hematological and non-hematological toxicities are defined differently.

5.5.1 Non-hematological dose-limiting toxicity

5.5.1.1 Any Grade 3 or greater non-hematological toxicity attributable to the protocol therapy with the specific exclusion of:

- Grade 3 nausea and vomiting < 3 days duration
- Grade 3 liver enzyme elevation, including ALT/AST/GGT, that returns to Grade ≤ 1 or baseline prior to the time for the next treatment cycle.
Note: For the purposes of this study the ULN for ALT is defined as 45 U/L and the ULN for AST is defined as 50 U/L, regardless of baseline. See [Appendix XV](#) for values that represent thresholds between CTCAE grades for ALT, AST, GGT and bilirubin.
- Grade 3 fever
- Grade 3 infection
- Grade 3 hypophosphatemia, hypokalemia, hypocalcemia or hypomagnesemia responsive to supplementation.
- Grade 3 or 4 hypertriglyceridemia that returns to Grade ≤ 2 prior to the start of the next treatment cycle. The severity (grade) of hypertriglyceridemia is based upon fasting levels. If Grade 3 or 4 triglycerides are detected when routine (non-fasting) laboratory studies are performed, the test should be repeated within 3 days in the fasting state to permit accurate grading (see [Section 6.4](#)).
- Grade 3 hyperglycemia that returns to a fasting glucose value ≤ 250 mg/dL or a fasting glucose of value ≤ 13.9 mmol/L (with or without the use of insulin or oral diabetic agents) prior to the start of the next treatment cycle. Medical management of hyperglycemia should be based on fasting levels. If routine (non-fasting) laboratory studies are performed and indicate the potential for intervention, the test should be repeated within 3 days in the fasting state to permit accurate medical management and grading (see [Section 6.6](#)).
- Grade 3 or 4 hypercholesterolemia that returns to \leq Grade 2 after initiation of lipid lowering medication prior to the next treatment cycle. The severity (grade) of hypercholesterolemia is based upon fasting levels. If Grade 3 or 4 hypercholesterolemia is detected when routine (non-fasting) laboratory studies are performed, the test should be repeated within 3 days in the fasting state to permit accurate grading (see [Section 6.5](#)).

5.5.1.2 Non-hematological toxicity that causes a delay of > 21 days between treatment cycles.

5.5.1.3 Note: Allergic reactions that necessitate discontinuation of study drug will

not be considered a dose-limiting toxicity.

5.5.2 Hematological dose limiting toxicity

In patients evaluable for hematological toxicity (see [Section 4.1.8.1](#)), hematological dose-limiting toxicity is defined as:

- Day 8:
 - Grade 4 neutropenia or platelets < 50,000/mm³ on Day 8 that does not resolve to ANC ≥ 750/mm³ and platelets ≥ 50,000/mm³ (transfusion independent) by Day 11 will be considered dose-limiting (see [Section 6.1](#)).
- Grade 4 thrombocytopenia (platelet count < 25,000/mm³) for ≥ 7 days
- Grade 4 anemia, not due to malignant infiltration.
- Grade 4 neutropenia that lasts for > 7 days
- Grade 3 thrombocytopenia with clinically significant bleeding, petechiae or purpura, or that persists for ≥ 7 days, and/or that requires platelet transfusion.
- Myelosuppression that causes a delay of > 21 days between treatment cycles.

Note: Grade 3 or 4 febrile neutropenia will not be considered a dose-limiting toxicity.

6.0 DOSE MODIFICATIONS FOR ADVERSE EVENTS

The Study Chair must be notified of any dosage modification or use of myeloid growth factor.

6.1 Dose Modification Guidelines for Cycle 1, Day 8

For Patients Evaluable for Hematological Toxicity:

Hematological Toxicity on Day 8: Thrombocytopenia	Action
Platelets ≥ 50,000/mm ³	
 • Continue protocol therapy.

Platelets < 50,000/mm³ without clinically significant bleeding, petechial or purpura
	
 • Patients who have platelets < 50,000/mm³ on Day 8 will have the dose of ABI-009 withheld. • If the toxicity resolves to platelets ≥ 50,000/mm³ (transfusion independent) by Day 11, the Day 8 dose of ABI-009 may be given. • If the toxicity does not resolve to platelets ≥ 50,000/mm³ by Day 11, the Day 8 dose of ABI-009 will be omitted and this will be considered a DLT. Patients should receive subsequent cycles of ABI-009 but at the next lower dose level or if the patient is being treated on the lowest dose level, protocol therapy should be discontinued.

Platelets < 50,000/mm³ with clinically significant bleeding, petechial or purpura
	
 • If Grade 3 thrombocytopenia with clinically significant bleeding, petechial or purpura, omit Day 8 dose of ABI-009, and this will be considered a DLT. Patients should receive subsequent cycles of ABI-009 but at the next lower dose level or if the patient is being treated on the lowest dose level, protocol therapy should be discontinued. • If persists for ≥ 7 days, patients should receive subsequent doses of ABI-009 at the next lower dose level or if the patient is being treated on the lowest dose level, protocol therapy should be discontinued.

Other thrombocytopenia DLTs per Section 5.5.2 on Day 8
	
 • As above, per platelet grade and bleeding.

Hematological Toxicity on Day 8: Neutropenia
	
Action

Grade 1-3
	
 • Continue protocol therapy.

Grade 4	
 • Patients who have Grade 4 neutropenia on Day 8 will have the dose of ABI-009 withheld. If the toxicity resolves to $ANC \geq 750/mm^3$ by Day 11, the Day 8 dose of ABI-009 may be given. • If the toxicity does not resolve to $ANC \geq 750/mm^3$ by Day 11, the Day 8 dose of ABI-009 will be omitted and this will be considered a DLT. Patients should receive subsequent cycles of ABI-009 but at the next lower dose level or if the patient is being treated on the lowest dose level, protocol therapy should be discontinued. • Patients who require that their Day 8 dose of ABI-009 be omitted for Grade 4 neutropenia after one dose reduction (if starting at DL - 1) or if the patient is being treated on the lowest dose level, protocol therapy should be discontinued.
Other neutropenia DLTs per Section 5.5.2 on Day 8	
 • As above in Grade 4 neutropenia.

Non-Hematological Toxicity on Day 8	Action
Grade 1-2	
 • Continue protocol therapy.
Grade 3-4	
 • Patients who have Grade 3 or Grade 4 non-hematological toxicity attributable to the study drug prior to the Day 8 dose (with the exception of the DLT exclusions in Section 5.5.1.1) will be considered to have had a DLT. If the toxicity resolves to meet eligibility or \leq Grade 2 (if not part of eligibility criteria) by Day 8, the dose of ABI-009 may be given but at the next lower dose level. • Patients who have Grade 3 or Grade 4 non-hematological toxicity attributable to the study drug on Day 8 prior to dosing (with the exception of the DLT exclusions in Section 5.5.1.1) will have their dose of ABI-009 withheld and this will be considered a DLT. If the toxicity resolves to meet eligibility or \leq Grade 2 (if not part of eligibility criteria) by Day 11, the Day 8 dose of ABI-009 may be given but at the next lower dose level. If the toxicity does not resolve by Day 11, the Day 8 dose of ABI-009 will be omitted. Patients should receive subsequent cycles of ABI-009 but with dose modifications according to Section 6.2 and Section 6.3.

6.2 Dose Modification Guidelines for Cycle 1

Hematological Toxicity: Thrombocytopenia	Action
Thrombocytopenia DLTs per Section 5.5.2	
 • Patients who have dose-limiting thrombocytopenia as defined in Section 5.5.2 should receive subsequent cycles at the next lower dose level of ABI-009; if the patient is being treated on the lowest dose level, protocol therapy should be discontinued. • Patients who experience dose-limiting thrombocytopenia after one dose reduction (if starting at DL -1) or if the patient is being treated on the lowest dose level, protocol therapy should be discontinued. • Patients who require that their Day 8 dose of ABI-009 be omitted for platelets < 50,000/mm³ (Section 6.1) after one dose reduction (if starting at DL -1) or if the patient is being treated on the lowest dose level, protocol therapy should be discontinued.

Hematological Toxicity: Neutropenia	Action

Neutropenia DLTs per Section 5.5.2
	
 • Patients who have dose-limiting neutropenia as defined in Section 5.5.2 with no other dose-limiting toxicity should receive the same dose of ABI-009 in the next cycle with myeloid growth factor support administered the next day after the Day 8 dose of ABI-009 is given during subsequent cycles (See Section 7.4). [Note: Patients MUST NOT receive prophylactic myeloid growth factor in the first cycle of therapy (See Section 7.4).] • If dose-limiting neutropenia recurs after myeloid growth factor is added, then the patient should be given the next lower dose level of ABI-009 followed by myeloid growth factor support beginning the next day after the Day 8 dose of ABI-009 is given for subsequent cycles (See Section 7.4). • Patients who experience dose-limiting neutropenia after the addition of myeloid growth factor and one dose reduction of ABI-009 must be removed from protocol therapy. • Patients who experience early dose-limiting neutropenia requiring the omission of the Day 8 dose of ABI-009 (as defined in Section 6.1) should receive subsequent cycles of protocol therapy but at the next lower dose level of ABI-009 or if the patient is being treated on the lowest dose level, protocol therapy should be discontinued. • Patients who require that their Day 8 dose of ABI-009 be omitted for Grade 4 neutropenia after one dose reduction (if starting at DL - 1) or if the patient is being treated on the lowest dose level, protocol therapy should be discontinued.
---	---

Other Hematological Toxicity	Action

Other hematologic DLTs per Section 5.5.2
	
 • Patients who have a dose-limiting hematological toxicity that does not resolve to meet eligibility or baseline parameters within 21 days after the planned start of the next treatment cycle must be removed from protocol therapy.

Non-Hematological Toxicity	Action
-----------------------------------	---------------

Non-hematological DLTs per Section 5.5.1
	
 • Patients who have any dose-limiting non-hematological toxicity (as defined in Section 5.5.1) may continue on protocol therapy upon meeting eligibility lab requirements or baseline but should receive subsequent doses at the next lower dose level of ABI-009. • If any non-hematological dose-limiting toxicity recurs after one dose reduction of ABI-009, the patient must be removed from protocol therapy. • Patients who have a dose-limiting non-hematological toxicity that does not resolve to baseline or eligibility within 21 days after the planned start of the next treatment cycle must be removed from protocol therapy.
---	---

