6.3 Dose Modification Guidelines for Cycle 2 or greater

Hematological Toxicity: Thrombocytopenia	Action
Platelets \geq 75,000/mm ³	
 • Continue protocol therapy.
Platelets < 75,000/mm ³	
 • ABI-009 as per Section 6.1 & Section 6.2. • Irinotecan & temozolomide will be continued at full dose.
Platelets < 50,000/mm ³	
 • ABI-009 as per Section 6.1 & Section 6.2. • Irinotecan & temozolomide will be continued at full dose.
Other thrombocytopenia DLTs per Section 5.5.2 on Day 8	
 • ABI-009 as per Section 6.1 & Section 6.2. • Irinotecan & temozolomide will be continued at full dose.

Hematological Toxicity: Neutropenia	Action
Grade 1-3	
 • Continue protocol therapy.
Grade 4	
 • ABI-009 as per Section 6.1 & Section 6.2. • Irinotecan & temozolomide will be continued at full dose.
Other neutropenia DLTs per Section 5.5.2 on Day 8	
 • ABI-009 as per Section 6.1 & Section 6.2. • Irinotecan & temozolomide will be continued at full dose.

Non-Hematological Toxicity	Action
Grade 1-2	
 Continue protocol therapy.
Grade 3-4	
 ABI-009 as per Section 6.1 & Section 6.2. Irinotecan & temozolomide will be continued at full dose.

Non-Hematological Toxicity	Action
Non-hematological DLTs per Section 5.5.1	
 ABI-009 as per Section 6.1 & Section 6.2. Irinotecan & temozolomide will be continued at full dose. Patients who experience dose-limiting non-hematological dose-limiting toxicity after one dose reduction (if starting at DL -1) or if the patient is being treated on the lowest dose level, protocol therapy should be discontinued. Patients who have a dose-limiting non-hematological toxicity that does not resolve to baseline or eligibility within 21 days after the planned start of the next treatment cycle must be removed from protocol therapy.

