10.0 CRITERIA FOR REMOVAL FROM PROTOCOL THERAPY AND OFF STUDY CRITERIA

10.1 Criteria for Removal from Protocol Therapy

- a) Clinical (including physical examination or serum tumor markers) or radiographic evidence of progressive disease (See [Section 12.0](#)).

- b) Adverse Events requiring removal from protocol therapy (See [Section 6.0](#)).
- c) Refusal of protocol therapy by patient/parent/guardian
- d) Non-compliance that in the opinion of the investigator does not allow for ongoing participation.
- e) Completion of 35 cycles of therapy.
- f) Physician determines it is not in the patient's best interest.
- g) Repeated eligibility laboratory studies (CBC with differential, bilirubin, ALT (SGPT) or serum creatinine) are outside the parameters required for eligibility prior to the start of ABI-009 (See [Section 8.1](#)).
- h) Study is terminated by Sponsor.
- i) Pregnancy

Patients who are removed from protocol therapy during cycle 1 should continue to have the required observations in [Section 8.1](#) until the originally planned end of the cycle or until all adverse events have resolved per [Section 13.4.4](#), whichever happens LATER. The only exception is with documentation of the patient's withdrawal of consent. Patients who are removed from protocol therapy in subsequent cycles should have the necessary observations to ensure adequate clinical care.

Patients who are off protocol therapy are to be followed until they meet the criteria for Off Study (see below). Ongoing adverse events, or adverse events that emerge after the patient is removed from protocol therapy, but within 30 days of the last dose of investigational agent, must be followed and reported via RAVE and CTEP-AERS (if applicable). Follow-up data will be required unless consent is withdrawn.

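### For a child at DL -2 who meets a platelet DLT before Day 8 and has platelets ≥ 50,000/mm³ on Day 8, Section 6.1 says to carry on and Section 6.2 says to stop

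*Combined protocol and SAP*

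**What the plan says.** Section 5.5.2 lists the hematological DLTs. Two of its platelet criteria need no minimum duration: Grade 3 thrombocytopenia with bleeding signs (clinically significant bleeding, or petechiae or purpura), and Grade 3 thrombocytopenia "and/or that requires platelet transfusion".

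Section 6.1 governs the Day 8 dose in Cycle 1. Its platelet table is headed "Hematological Toxicity on Day 8: Thrombocytopenia" and is organised by the count on that day. The row for ≥ 50,000/mm³ says only "Continue protocol therapy". The row for other thrombocytopenia DLTs says "As above, per platelet grade and bleeding".

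The non-hematological part of 6.1 is built differently. It has a separate instruction for a dose-limiting event that arose "prior to the Day 8 dose": if the event has resolved, the dose may be given, but one level down.

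Section 6.2 covers Cycle 1 as a whole. For a patient with a 5.5.2 platelet DLT it says that "if the patient is being treated on the lowest dose level, protocol therapy should be discontinued". Its first bullet places the alternative, a dose reduction, in later cycles. Its second bullet repeats the stop at the lowest level without mentioning later cycles.

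Section 6.3 covers Cycle 2 onward. Its rows for lower counts, and its row for other platelet DLTs on Day 8, say "ABI-009 as per Section 6.1 & Section 6.2". Its row for ≥ 75,000/mm³ only says to continue.

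Section 10.1(b) makes "Adverse Events requiring removal from protocol therapy" a ground for removal and refers to Section 6.0 for what those are. Under Amendment #4 (Sections 5.1.1 and 5.3.1), patients start at DL -2, 15 mg/m², with no level below it.

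**The concern.** The Day 8 platelet table looks only at the count on the day. A child may have met a platelet DLT a few days earlier and since recovered, or been transfused, to 50,000/mm³ or more. That child fits the first row and is cleared for the second ABI-009 dose of the cycle, unreduced. Section 6.2 takes the same child off therapy. A clinician using the table written for that day's decision and one using the general Cycle 1 rule would therefore act in opposite ways on whether to re-dose a child after a DLT.

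The conflict matters more since Amendment #4. At a higher level, 6.2 would lead to a dose reduction. At DL -2 it leads to discontinuation, and every new patient starts at DL -2.

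**Working it through.** No plan figure has to be reproduced. The check follows one child through the rules and then sizes the dose at stake.

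**Illustrative child at DL -2:** platelets 30,000/mm³ on Day 5, platelet transfusion required, event attributable to therapy, 60,000/mm³ on Day 8, no bleeding. (Grade 4 in 5.5.2 begins below 25,000/mm³, so 30,000 is taken as Grade 3.)

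1. *Section 5.5.2.* Grade 3 thrombocytopenia requiring transfusion: a DLT on Day 5.
2. *Section 6.1, Day 8.* 60,000 ≥ 50,000, so the first row applies: continue. The row for other platelet DLTs sends the reader back to the same count and bleeding rows, so it does not change the result.
3. *Section 6.2.* Platelet DLT at the lowest level: discontinue.
4. *Section 10.1(b).* Refers back to Section 6.0 and does not rank 6.1 against 6.2.

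The result is the same if the Day 5 event is Grade 3 with purpura that recovers to ≥ 50,000/mm³ by Day 8.

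**Comparison within 6.1.** Grade 3 with bleeding signs and a count still below 50,000/mm³ on Day 8: omit the dose and, at the lowest level, discontinue. Here 6.1 and 6.2 agree. The same DLT with a Day 8 count just above 50,000/mm³: continue. The child's DLT status is identical; only the Day 8 count differs.

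**A second, very narrow route.** A child whose DLT was a transfusion without bleeding, and whose count is below 50,000/mm³ on Day 8, is sent by the other-DLT row to the non-bleeding row. That row allows the dose on transfusion-independent recovery by Day 11, although 6.2 says to stop.

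**Can the earlier event be seen in time?** Section 8.1 schedules blood counts every 3 to 4 days in Cycles 1 and 2. Counting from Day 1, every 3 days gives Days 4 and 7; every 4 days gives Day 5. So there are one or two scheduled counts before the Day 8 decision.

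**Dose at stake.** ABI-009 is given on Days 1 and 8: 15 / (15 + 15) = 50% of the cycle's ABI-009. This is the size of the dose in one case, not a frequency.

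**Frequency.** Section 2.6 reports 2 platelet DLTs among 5 patients enrolled at DL 1 and 2 among 6 evaluable at DL -1, 2 + 2 = 4 in all. None is dated relative to Day 8, and DL -2 uses modified hematological DLT definitions. No rate can be derived.

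**The case against.** The best defence is that 6.1 and 6.2 apply together. Section 6.1 is a Day 8 gate for children still on therapy. Section 6.2 applies to any platelet DLT in the cycle, and its second bullet states the stop at the lowest level without mentioning later cycles or recovery. Section 10.1(b) makes that a removal criterion. Section 6.3 names 6.1 and 6.2 jointly. On this reading a child with a DLT on Day 5 is already off therapy on Day 8, and only a cross-reference is missing. There are also safeguards: a suspected DLT goes to the Study Chair within 24 hours (5.4), a weekly call reviews DLTs (14.4.2), and the physician may withdraw a patient (10.1(f)).

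Much of this stands. The plan does contain the right action, and the joint reading is plausible. It is not compelled. The first 6.2 bullet speaks of later cycles, so a site could give the Day 8 dose and stop afterwards. The non-hematological part of 6.1 also shows that an event before Day 8 was thought to need its own instruction there. The safeguards are real, but none states the dosing action.

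A reader might infer three stronger points, which the documents do not support:

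- *That no transfused count should pass the ≥ 50,000/mm³ row.* A platelet transfusion given above 50,000/mm³, for example before a procedure, is not a DLT under 5.5.2, and 6.2 does not stop that child. Limiting the row to transfusion-independent counts would leave the child with no row. Withholding the dose would leave 50% of the Cycle 1 dose against the 85% required by 11.2.1. Unless the per-protocol wording there excuses the omission, the child would be replaced, in a trial where 7 of 13 patients at DL -1 were already inevaluable.
- *That 6.3 repeats the gap in every row.* Only its ≥ 75,000/mm³ row lacks a pointer; its lower-count rows and its other-DLT row send the reader to both 6.1 and 6.2.
- *That the four reported DLTs show this happening.* They are not timed against Day 8.

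**Conclusion.** The point holds as a conflict between two stated dosing rules, limited to one situation: a child at DL -2 whose platelet DLT before Day 8 was Grade 3 with bleeding signs or requiring transfusion, and whose Day 8 count is ≥ 50,000/mm³. The narrow route through the other-DLT row is a lesser instance. The event of 7 days or more is not included, because 6.1 can be read to give it the same action as 6.2.

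The consequence is a possible unreduced 15 mg/m² dose to a child whom another section takes off therapy. The case is rare, because in Cycle 1 it needs a fall from an entry count of at least 100,000/mm³ to a dose-limiting Grade 3 event after one dose, and then recovery by Day 8; its frequency is unknown. The child counts as a DLT on either reading, so the DLT count and the MTD decision are unaffected.

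The conclusion assumes that the event is attributed to protocol therapy and that no rule outside these documents ranks 6.1 and 6.2. It is a safety clarification that should be made, and it does not challenge the design.

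**What to change.** Add to the thrombocytopenia table in Section 6.1, and use in place of the present text of the row for other platelet DLTs:

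*A patient who has already met a Section 5.5.2 platelet DLT in this cycle does not receive the Day 8 dose of ABI-009, whatever the Day 8 count, and follows Section 6.2 (next lower dose level in subsequent cycles; discontinue protocol therapy if on the lowest dose level).*

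Add a cross-reference to this rule in the ≥ 75,000/mm³ row of Section 6.3. Leave the ≥ 50,000/mm³ row otherwise as it is, with no general transfusion restriction.

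The cost is one sentence, one replaced row and one cross-reference, with no added tests. A few children whose counts have recovered would lose one Day 8 dose. They already count as DLTs, and 11.2.1 replaces only patients without a DLT, so no patients are added.

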Amendment #4: ABI-009 will be administered intravenously over 30 minutes on Day 1 and Day 8 of each cycle (beginning at Dose Level -2 = 15 mg/m²/dose; see dose escalation table in [Section 5.3.1](#)). ABI-009 should be given within 8 hours following administration of temozolomide and irinotecan. The use of in-line filters is NOT necessary. Upon completion of infusion, the infusion catheter should be flushed with normal saline.

Cefixime or an available equivalent antibiotic will be used as diarrheal prophylaxis for cycles 2+. Initiation of antibiotic treatment two days prior to the start of irinotecan is required, and will continue during, and 3 days after the last dose of irinotecan of each cycle. This antibiotic therapy will continue throughout protocol therapy. Cefixime will be dosed at 8 mg/kg PO once daily (max: 400 mg/day). If cefixime is not available, cefpodoxime can be used as an alternative at 5 mg/kg/dose PO twice daily (10 mg/kg/day in two divided doses; max: 200 mg/dose).

Note: Patients **must** also receive pneumocystis prophylaxis during study therapy for cycles 2+.

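### For patients starting at DL -2, three dose-modification rules in 6.1 and 6.2 order a reduction to a level that does not exist, and 6.3 is inconsistent for non-hematological DLTs

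*Combined protocol and SAP*

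**What the plan says.** **Starting level.** Section 5.1.2 describes Amendment #4 dosing as "beginning at Dose Level -2 = 15 mg/m²/dose". The dose table in 5.3.1 marks that row "Amendment #4: Starting dose level" and has no row beneath it. Section 11.3.1 enrolls Amendment #4 patients at DL -2.

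**Rules that order a reduction without providing for the lowest level.**

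- Section 6.1, non-hematological Grade 3-4 toxicity that occurs before Day 8 and resolves by then: "the dose of ABI-009 may be given but at the next lower dose level". The companion bullet, for toxicity present on Day 8 that resolves by Day 11, also allows the dose only at a reduced level.
- Section 6.2, non-hematological DLT: the patient may continue but "should receive subsequent doses at the next lower dose level of ABI-009".
- Section 6.2, dose-limiting neutropenia that recurs once growth factor has been added: "then the patient should be given the next lower dose level of ABI-009 followed by myeloid growth factor support".

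**Cycle 2 or greater.** The non-hematological DLT row of 6.3 first handles ABI-009 by reference to 6.1 and 6.2. A later bullet in the same row adds "or if the patient is being treated on the lowest dose level, protocol therapy should be discontinued". The neutropenia rows of 6.3 that restrict dosing give no ABI-009 rule of their own and only refer back.

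**The concern.** A patient who starts at DL -2 and has a non-hematological DLT in Cycle 1 is told that treatment may go on, but only at a dose the protocol does not define. One site could stop and another could re-treat at 15 mg/m². Neither would be following a written rule for that situation.

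This is first a safety matter, because a stated protective rule cannot be carried out. It also affects the data. Toxicity of the combination (aim 1.1.3) and ABI-009 pharmacokinetics (aim 1.1.4) are primary aims, the combination begins in Cycle 2, and 8.3.2.1 schedules ABI-009 sampling in Cycle 2. If sites handle these patients differently, who contributes Cycle 2 exposure and toxicity data after such a toxicity depends partly on the site's reading of the tables.

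**Working it through.** No sample size, error rate or event count bears on this point. The check takes a patient who starts at DL -2 and reads each rule against the dose table in 5.3.1. Levels in that table: 15, 20, 35, 45 and 55 mg/m². Levels below 15 mg/m²: none.

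| Rule | ABI-009 instruction | Provides for lowest level? | Result for a DL -2 starter |
|---|---|---|---|
| 6.1 thrombocytopenia; 6.1 Grade 4 neutropenia with Day 8 dose omitted | Reduce | Yes | One instruction |
| 6.1 non-hematological Grade 3-4 (both bullets) | Reduce | No | No level to go to |
| 6.2 thrombocytopenia; 6.2 neutropenia with Day 8 dose omitted | Reduce | Yes | One instruction |
| 6.2 neutropenia recurring after growth factor | Reduce | No | No level to go to |
| 6.2 non-hematological DLT | Reduce | No | No level to go to |
| 6.3 Grade 4 and other dose-limiting neutropenia | Refer to 6.1 and 6.2 | No | Inherits the 6.2 gap |
| 6.3 non-hematological DLT | Refer to 6.1 and 6.2; also discontinue at lowest level | Yes | Two instructions |
| 6.4, 6.5, 6.6 | Reduce under stated conditions | Yes, in each section | Provided for |

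**Do the removal rules close the gap?**

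1. In 6.2, removal for a recurrent non-hematological DLT applies after one dose reduction.
2. In 6.2, removal for recurrent neutropenia applies after growth factor and one dose reduction.
3. A patient who starts at the lowest level cannot have had a reduction, so read literally neither condition can be met.
4. The separate 6.2 rule that removes patients whose DLT has not resolved within 21 days of the planned next cycle needs no reduction and still works. It does not help a patient whose toxicity resolves.
5. Section 10.1 gives no independent rule: its adverse-event criterion points back to Section 6.0. It does leave room for physician judgment, but that is not a uniform instruction.

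**Gap or conflict?** For non-hematological DLTs, the 6.3 row imports 6.1 and 6.2 and then adds its own discontinuation rule, so there is both a gap and an inconsistency. For recurrent neutropenia, 6.3 leads back to 6.2, so there is a gap only.

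**The case against.** **Cycle headings.** Sections 6.1 and 6.2 are headed for Cycle 1 and 6.3 for Cycle 2 or greater. The lowest-level bullet in 6.3 can be read as qualifying its general cross-reference, and 6.1 sends patients whose Day 8 toxicity has not resolved to both 6.2 and 6.3. This is a fair reading and softens the inconsistency. It does not supply an instruction in the 6.1 and 6.2 rows, and it does not reach neutropenia.

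**Oversight.** Suspected DLTs go to the Study Chair within 24 hours (5.4), dose modifications must be notified (6.0), and the Study Chair's evaluations are reviewed weekly (14.4.2). Unnoticed divergence between sites is therefore unlikely. This lowers the risk but does not replace a written rule.

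**Stronger readings that a reader might infer, and that the documents do not support:**

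- *That 6.3 orders discontinuation for recurrent neutropenia.* It does not; its neutropenia rows only refer back.
- *That the parenthetical about starting at DL -1 is outdated.* It fits the amended table: a DL -1 starter can drop once, to DL -2. DL -2 starters are covered by the lowest-level words that follow it. Changing it to DL -2 would presuppose a reduction that cannot occur.
- *That 5.3.1 itself settles individual dosing.* The statement "there will be no planned escalations beyond dose level -2. If DL -2 is not well tolerated further de-escalation will not occur" stands under inter-patient escalation and concerns the cohort. It confirms that no lower level is planned, but it is not a rule for one patient's dose.
- *That every new patient is affected.* Section 11.1.1 projects 18 additional patients, at most 26. These are enrollment totals that include a 30% allowance for inevaluable patients, not counts of patients with these toxicities.

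**Conclusion.** The point holds within limits. For a patient at DL -2, the non-hematological Grade 3-4 rules of 6.1, the non-hematological DLT rule of 6.2 and the recurrent-neutropenia rule of 6.2 cannot be carried out as written. Section 6.3 is inconsistent for non-hematological DLTs only.

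The number affected should be small, but the documents give no rate from which to estimate it. All four DLTs reported in 2.6 (two at DL 1 and two at DL -1) were platelet decreases, and the thrombocytopenia rows do cover the lowest level. Under 11.3.1, two or more patients with DLT among six evaluable close accrual. Earlier patients dosed at DL 1 or DL -1 have a lower level in the amended table.

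The tolerability decision is largely protected: under 11.2.1 and 11.2.2 a patient with a DLT is evaluable and counted whatever is given afterwards. What remains exposed is the safety of the affected patients and the consistency of later-cycle toxicity and exposure data. The conclusion assumes that no dose below 15 mg/m² is defined elsewhere; the available text shows none.

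**What to change.** Reconcile the following with the dose table in 5.3.1, so that each gives one instruction for a patient already at the lowest level:

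- the two non-hematological Grade 3-4 bullets in 6.1;
- the non-hematological DLT row in 6.2, including its removal rule for recurrence;
- the bullet in 6.2 on neutropenia recurring after growth factor, and the removal bullet after it;
- the non-hematological DLT row in 6.3, so that its cross-reference and its lowest-level bullet agree.

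Which instruction applies is for the sponsor to decide. Leave the qualifiers about starting at DL -1 unchanged. The cost is table wording in an amendment; sample size, the DLT definition and the analysis are unaffected.
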